### **Mean weekly dose of low potency TCS**

The mean weekly dose of low potency TCS use during the treatment period endpoints will be analyzed using an ANCOVA model with treatment, randomization strata (baseline weight group, disease severity and region) and relevant baseline variables included in the model.

Similar analysis will be carried out for medium and/or high potency TCS.

Descriptive statistics will be provided for the mean of caregiver missed workdays (CMW) from baseline to week 16 for each treatment group.

### **Onset of action analysis,**

Onset of action in percent change from baseline weekly average of daily worst scratch/itch NRS score can be assessed by providing a nominal p-value at each assessment visits. The analysis will be carried out on the FAS population only. Using this analysis, the first assessment visit at which  $p < 0.05$  for the difference from placebo in the weekly average of daily worst scratch/itch NRS

score that remains  $p < 0.05$  at subsequent weekly measurements through week 16 can be identified. The similar analysis will be carried out on the following binary responses:

- IGA 0/1
- EASI-75
- Improvement (reduction) of weekly average of daily worst itch NRS score  $\geq 3$  from baseline
- Improvement (reduction) of weekly average of daily worst itch NRS score  $\geq 3$  from baseline.

### **5.6.3. Adjustment for Multiple Comparison**

#### Multiplicity Considerations

The following multiplicity adjustment approach, a hierarchical procedure, will be used to control the overall Type-1 error rate at 0.05 for the primary endpoint and the secondary endpoints of dupilumab versus placebo. Each hypothesis will be formally tested only if the preceding one is significant at the 2-sided 0.05 significance level. The hierarchical testing order is shown in below table (all comparisons are with the placebo).

Level	Endpoints	Testing Order
Primary endpoint	Proportion of patients with IGA 0 to 1 (on a 5-point scale) at week 16	1
Co-primary endpoint for EMA and EMA Reference Market Countries only, key secondary for US	Proportion of patients with EASI-75 ( $\geq 75\%$ improvement from baseline) at week 16	2
Secondary endpoints	Percent change in EASI score from baseline to week 16	3
	Percent change from baseline to week 16 in weekly average of daily worst scratch/itch score	4
	Proportion of patients with improvement (reduction) of weekly average of daily worst itch score $\geq 4$ from baseline	5
	Proportion of patients with improvement (reduction) of weekly average of daily worst itch score $\geq 3$ from baseline	6
	Proportion of patients with EASI-50 at week 16	7
	Proportion of patients with EASI-90 at week 16	8
	Change from baseline in percent BSA affected by AD	9
	Change from baseline to week 16 in POEM	10
	Percent change from baseline to week 16 in SCORAD	11
	Change from baseline in Patient's sleep quality NRS	12
	Change from baseline in Patient's skin pain NRS	13
	Change from baseline in DFI	14
	Change from baseline to week 16 in CDLQI	15
	Change from baseline to week 16 in IDQOL	16

#### 5.6.4. Subgroup Analysis

Subgroups for the primary endpoint (or co-primary endpoints for EU and EU reference countries) and key secondary endpoints will be analyzed based on the FAS.

Primary endpoints (or co-primary endpoints for EU and EU reference countries) and secondary endpoints those are in the hierarchical procedure (Section 5.6.3) will be analyzed in a similar fashion as in the main analysis for the severe AD subgroup (IGA = 4). Nominal p-values will be provided.

The analysis method for the subgroups will be the same as the primary analysis described in Section 5.6.1, and Section 5.6.2, as appropriate. If for any reason such as due to small number of patients in a subgroup, the model-based inferential statistics cannot be computed, or deemed inappropriate, only descriptive statistics will be provided.

Forest plots of the co-primary and key secondary efficacy endpoints across subgroups will be provided.

### **5.6.5. Analyses of Other Efficacy Variables**

The analyses of other efficacy variables (binary and continuous endpoints) will be conducted in a similar fashion as the primary analysis described in Sections 5.6.1 and 5.6.2, unless otherwise noted in the individual descriptions of other efficacy variables or deemed inappropriate.

## **5.7. Analysis of Safety Data**

The analysis of safety and tolerability will be performed based on the SAF.

The safety analysis will be based on the reported AEs, clinical laboratory evaluations, physical examination, vital signs and 12-lead ECG.

Thresholds for treatment-emergent Potentially Clinically Significant Values (PCSVs) in laboratory variables and vital signs are defined in Appendix 5. A treatment-emergent PCSV is any PCSV which developed or worsened in severity compared to baseline during the treatment and/or follow-up period. The time interval to detect any event or abnormality is between the first injection of study medication and EOS.

In addition, the summary of safety results (including TEAEs, clinical laboratory, vital signs and ECG) will be performed for subjects who were impacted by COVID-19 pandemic and not impacted by COVID-19 pandemic in each study part, respectively if deemed appropriate. The summary will be performed for pre-, during, and post-COVID-19 periods for patients impacted by COVID-19, if deemed appropriate.

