9.5.3.1. Adverse Events

Definitions

For safety variables, 2 observation periods are defined separately for parts A and B:

- The pre-treatment period is defined as the time from signing the ICF to before the first dose of study drug.
- The treatment-emergent period is defined as the day from the first dose of study drug to the end of the study. In Part B, the treatment-emergent period includes the 16-week treatment period and follow-up period.
 - Treatment period: date of the first dose of study drug to week 16 visit date (study day 113 starting from the first dose of study drug if week 16 visit date is unavailable) or early termination date, whichever comes first.
 - Follow-up period: date after week 16 visit date (study day 113 starting from first dose of study drug if week 16 visit date is unavailable) or early termination date, to end of study. Patients who continue into the OLE after the treatment period will not have a follow-up period.

Treatment-emergent AEs are defined as those that are not present at baseline or represent the exacerbation of a pre-existing condition during the overall study period.

Analysis

All AEs reported in this study will be coded using the currently available version of the Medical Dictionary for Regulatory Activities (MedDRA®). Coding will be to lowest level terms. The verbatim text, the preferred term (PT), and the primary system organ class (SOC) will be listed.

Summaries of all TEAEs by treatment group will be provided separately for parts A and B. The summary will include:

- The number (n) and percentage (%) of patients with at least 1 TEAE by SOC and PT
- TEAEs by severity (according to the grading scale outlined in Section 7.3.1), presented by SOC and PT
- TEAEs by relationship to treatment (related, not related), presented by SOC and PT

Deaths and other SAEs will be listed and summarized by treatment group.

Treatment-emergent adverse events leading to permanent treatment discontinuation will be listed and summarized by treatment group.

In addition, to account for potential differential exposure time, the exposure-adjusted analyses for part B may be provided. The details will be specified in the SAP.

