### 2.4. Study Plan (Part B)

The study consists of the following periods (Figure 3):

1. Screening of up to 56 days, including TCS standardization period of 2 weeks
2. Treatment period of 16 weeks, and
3. Follow-up of 12 weeks (for patients who do not enter the OLE study, R668-AD-1434)

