**Figure 3: Study Flow Diagram**

TCS Std: topical corticosteroid standardization

Note: The length of the screening period is not fixed but must not exceed 56 days (including TCS standardization). The length of the TCS standardization period is fixed at 14 days. Moisturizers are to be applied at least twice daily during the 7 consecutive days prior to randomization (not including day of randomization) and are to be used throughout the study. At least 11 of the 14 total applications of moisturizers prior to randomization must be applied for the patient to remain eligible for the study.

Starting on day -14, all patients will be required to initiate treatment with low potency TCS using a standardized regimen (see Section 5.2 for details).

During the treatment period, patients will have in-clinic visits at baseline, week 1, week 2, and week 4, then monthly in-clinic visits through week 16 with weekly telephone visits in between the clinic visits.

Safety and laboratory assessments, samples for dupilumab concentration and ADA response to dupilumab, and efficacy assessments will be performed or collected at specified time points throughout Part B of the study according to the schedule described in study protocol. The end of treatment period visit will occur at week 16, 4 weeks after the last dose of study drug. The primary endpoint (and co-primary endpoint for EU and EU Reference Market Countries only, proportion of patients with an EASI-75, which is a key secondary endpoint for US) will be assessed at this visit.

An OLE study (R668-AD-1434) in patients aged 6 months to <18 years old is currently ongoing. Patients who complete the treatment period in Part B may subsequently be eligible to participate in the OLE study (refer to R668-AD-1434 Protocol).

Patients who decline to participate in the OLE will enter a follow-up period of 12 weeks. Follow up visits will occur every 4 weeks from week 20 through week 28. During the follow-up period, patients will be monitored for safety and tolerability and have laboratory and clinical assessments

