### **5.7.1. Adverse Events**

The number and proportion of patients reporting TEAEs will be summarized overall during the study, during the week 16 treatment period, and during the follow-up period separately, sorted by decreasing frequency of SOC and PT in the dupilumab group.

AE incidence tables will be presented by treatment group for the SAF as well as for selected subgroups. TEAE summaries will present the number (n) and percentage (%) of subjects experiencing a TEAE by SOC and PT, sorted by decreasing frequency of SOC and PT for the dupilumab treatment group. Multiple occurrences of AEs of the same PT (or SOC) in the same subject will be counted only once for that PT (or SOC). For tables presenting severity of events, the worst severity will be chosen for subjects with multiple instances of the same event. The denominator for computation of percentage is the number of patients in each treatment group for the corresponding analysis period as specified in Section 3.2.

An overall summary of TEAEs will be provided with number and proportions of patients with any:

- TEAE
- Serious TEAE
- TEAE of special interest (AESI)

- TEAE leading to death
- TEAE leading to permanent treatment discontinuation

Detailed summaries of TEAEs will include:

- TEAEs
  - TEAEs by SOC/PT
  - TEAEs (for HLTs: Injection site reactions, Herpes viral infections) by SOC/HLT/PT
  - TEAEs by PT
  - Common TEAEs by SOC/PT (incidence with PT  $\geq 5\%$ )
  - TEAEs by severity by SOC/PT
  - Severe TEAEs by SOC/PT
  - TEAEs related to study medication as assessed by the investigator by SOC/PT
  - Severe TEAEs related to study medication as assessed by the investigator by SOC/PT
- Serious TEAEs by SOC/PT
  - Serious TEAEs by SOC/PT
  - Serious TEAEs by SOC/PT
  - Serious TEAEs related to study medication as assessed by the investigator by SOC/PT
- TEAEs leading to permanent discontinuation of study treatment by SOC/PT
- Fatal TEAE by SOC/PT
- AESI by AESI category ([Appendix 4](#)) and HLT/PT

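### Potentially clinically significant values (PCSVs) are counted to end of study, a window about 12 weeks longer for children who enter follow-up than for those who enter the open-label extension (OLE)

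*SAP*

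**What the plan says.** - **PCSV interval.** SAP 5.7 defines a treatment-emergent PCSV as one that "developed or worsened in severity compared to baseline during the treatment and/or follow-up period", and adds: "The time interval to detect any event or abnormality is between the first injection of study medication and EOS".
- **PCSV tables.** SAP 5.7.2 (laboratory), 5.7.3 (vital signs) and 5.7.4 (ECG, depending on the data) each call for the number and percentage of patients with a PCSV. None names an analysis period. A note to Table 4 in SAP 6.4 lets unscheduled values count as well as scheduled ones.
- **Who is followed past week 16.** SAP 2.4 states: "Patients who decline to participate in the OLE will enter a follow-up period of 12 weeks". Protocol 9.5.3.1 states: "Patients who continue into the OLE after the treatment period will not have a follow-up period".
- **Timing of the last dose.** From SAP 2.4: "The end of treatment period visit will occur at week 16, 4 weeks after the last dose of study drug".
- **Periods defined elsewhere.** SAP 3.2 sets up three periods for safety summaries: 16-week treatment, follow-up and overall study. It limits follow-up analyses to children who entered follow-up and had a visit after week 16. SAP 5.7.1 uses these periods for treatment-emergent adverse events (TEAEs), which are "summarized overall during the study, during the week 16 treatment period, and during the follow-up period separately". The hazard ratios in the same section use the treatment period only.

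**The concern.** A child's chance of being flagged at least once rises with the number of times the child is checked. Under the only interval stated for PCSVs, a child who enters follow-up has more checks than a child who enters the OLE. The OLE decision comes after 16 weeks of randomised treatment and may be related to arm through response or tolerability, so randomisation does not guarantee that the windows balance.

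The follow-up values are also taken after dosing has ended, while drug concentrations are declining, yet they are pooled with values taken on treatment.

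What is at stake is the reading of the by-arm laboratory, vital-sign and ECG PCSV tables. No hypothesis test on PCSVs is planned, so this concerns a descriptive safety comparison and not the trial's primary conclusion.

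**Working it through.** **1. The two windows.** With study day = 7 × week + 1, week 16 is day 7 × 16 + 1 = 113 and week 28 is day 7 × 28 + 1 = 197. Both match the target days in SAP 6.4. The window for a child who enters follow-up is 197 − 113 = 84 days longer (197/113 = 1.74 times as long). The last planned dose is at week 12, day 85. Week 16 is therefore 28 days after it, and week 28 is 112 days after it.

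**2. Scheduled checks after the baseline visit** (Protocol Table 2; SAP Appendix 3).

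| Measure | Weeks | OLE entrant | Enters follow-up |
|---|---|---|---|
| Hematology and chemistry | 4, 16, 28 | 2 | 3 |
| Vital signs | 1, 2, 4, 8, 12, 16, 20, 24, 28 | 6 | 9 |
| ECG | 16, 28 | 1 | 2 |

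**3. Chance of at least one PCSV.** The documents give no PCSV rates. Assume a chance p at each check, independent between checks and the same in both arms (no drug effect). Then P(at least one) = 1 − (1 − p)^m for m checks. For laboratory sets:

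- p = 5%: 1 − 0.95² = 9.8% versus 1 − 0.95³ = 14.3%, a gap of 4.5 points
- p = 10%: 1 − 0.90² = 19.0% versus 1 − 0.90³ = 27.1%, a gap of 8.1 points
- p = 20%: 1 − 0.80² = 36.0% versus 1 − 0.80³ = 48.8%, a gap of 12.8 points

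At p = 5%, vital signs give 26.5% versus 37.0%, and ECG gives 5.0% versus 9.75%.

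**4. Artefact between arms.** With no drug effect, the spurious difference is the gap in step 3 times the difference in OLE uptake between arms. The arm with lower uptake shows the excess. The documents give no uptake figures, so a range is assumed.

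| Laboratory p | Uptake differs by 10 points | 20 points | 30 points |
|---|---|---|---|
| 5% | 0.5 | 0.9 | 1.4 |
| 10% | 0.8 | 1.6 | 2.4 |
| 20% | 1.3 | 2.6 | 3.8 |

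Entries are percentage points. For rarer PCSVs (p = 1% to 5%) and an assumed uptake of 95% versus 75%, the artefact is 0.2 to 0.9 points for laboratory sets, 0.6 to 2.1 for vital signs and 0.2 to 0.95 for ECG. The largest of these, 2.1 points, is about 1.7 children per 80. If uptake and follow-up rates are equal between arms, the artefact is zero.

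**5. Effect of pooling follow-up values.** Take assumed chances per laboratory set of 10% versus 5% on treatment (two sets) and 5% in both arms at week 28, with every child followed to week 28. The risk difference to week 16 is 19.0% − 9.75% = 9.25 points. To week 28 it is (1 − 0.90² × 0.95) − (1 − 0.95³) = 23.05% − 14.26% = 8.79 points. The risk ratio moves from 1.95 to 1.62. Pooling hardly changes the difference but pulls the ratio towards 1.

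**The case against.** The strongest reply is that the SAP 5.7 sentence is only the outer bound of treatment-emergent. It covers any event as well as any abnormality, and adverse events are still split by period in the next subsection. SAP 3.2 defines its periods for safety summaries generally, and Protocol 9.5.3.1 itself includes follow-up in the Part B treatment-emergent period. A reader might infer that 5.7 overrides SAP 3.2. The text does not support that, and a 16-week PCSV table would be consistent with the SAP. What remains is that nothing applies the 3.2 periods to PCSVs, and the only interval stated for them runs to end of study.

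A reader might also infer that the SAP dropped a required exposure adjustment. The protocol says only that "to account for potential differential exposure time, the exposure-adjusted analyses for part B may be provided". That is optional, and it sits under adverse events. The protocol's laboratory and vital-sign text (9.5.3.2) has no such provision.

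A third tempting reading is that follow-up values are off-drug and so hide a drug effect. Protocol 1.2.1 chose the 12-week follow-up to let concentrations fall to non-detectable levels in most patients, so some drug remains early in follow-up. Pooling removes no on-treatment case, and step 5 shows little movement in the risk difference.

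It is also fair that by-visit laboratory and vital-sign summaries are unaffected. SAP 5.4 and 5.5.2 will show OLE entry and observation time by arm, so imbalance will be visible, although the PCSV table itself would not be corrected for it. Repeat tests in one child are probably positively correlated, which would shrink the step 3 gaps.

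**Conclusion.** The point holds as a minor one. If the stated interval is followed, by-arm PCSV percentages cover windows of about 113 or 197 days, depending partly on OLE entry after randomisation. OLE eligibility and early withdrawal also affect the window, so it is not a matter of choice alone.

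The documents do not show that the comparison is biased. That requires OLE uptake, or the PCSV rate during follow-up, to differ by arm, and neither is given. If uptake differs by 10 to 30 points, the artefact is about 0.5 to 4 percentage points or less. That figure assumes independent checks, per-check chances up to 20% for laboratory sets and 5% for vital signs and ECG, and scheduled visits only. The unequal windows come from the documents themselves; the size of any artefact rests on these assumptions.

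**What to change.** State in SAP 5.7, and in 5.7.2 to 5.7.4, that the between-arm number and percentage of patients with treatment-emergent PCSVs is reported for the 16-week treatment period of SAP 3.2. Show follow-up PCSVs separately, in the follow-up subset defined there. Label any overall-study PCSV table as supplementary.

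Every child who completes the treatment period then has the same scheduled checks after baseline (2 laboratory sets, 6 vital-sign visits, 1 ECG), whatever the OLE decision. Windows still differ for children who terminate early.

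No exposure-adjusted PCSV rate is needed. It would fit poorly in any case, because the only laboratory set and ECG scheduled after week 16 are at week 28, so onset within those 12 weeks is unknown.

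The cost is a sentence or two of SAP text and a period filter on tables already planned. No data are added or lost, and PCSV reporting then matches TEAE reporting.

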### **5.7.1. Adverse Events**

The number and proportion of patients reporting TEAEs will be summarized overall during the study, during the week 16 treatment period, and during the follow-up period separately, sorted by decreasing frequency of SOC and PT in the dupilumab group.

AE incidence tables will be presented by treatment group for the SAF as well as for selected subgroups. TEAE summaries will present the number (n) and percentage (%) of subjects experiencing a TEAE by SOC and PT, sorted by decreasing frequency of SOC and PT for the dupilumab treatment group. Multiple occurrences of AEs of the same PT (or SOC) in the same subject will be counted only once for that PT (or SOC). For tables presenting severity of events, the worst severity will be chosen for subjects with multiple instances of the same event. The denominator for computation of percentage is the number of patients in each treatment group for the corresponding analysis period as specified in Section 3.2.

An overall summary of TEAEs will be provided with number and proportions of patients with any:

- TEAE
- Serious TEAE
- TEAE of special interest (AESI)

- TEAE leading to death
- TEAE leading to permanent treatment discontinuation

Detailed summaries of TEAEs will include:

- TEAEs
  - TEAEs by SOC/PT
  - TEAEs (for HLTs: Injection site reactions, Herpes viral infections) by SOC/HLT/PT
  - TEAEs by PT
  - Common TEAEs by SOC/PT (incidence with PT  $\geq 5\%$ )
  - TEAEs by severity by SOC/PT
  - Severe TEAEs by SOC/PT
  - TEAEs related to study medication as assessed by the investigator by SOC/PT
  - Severe TEAEs related to study medication as assessed by the investigator by SOC/PT
- Serious TEAEs by SOC/PT
  - Serious TEAEs by SOC/PT
  - Serious TEAEs by SOC/PT
  - Serious TEAEs related to study medication as assessed by the investigator by SOC/PT
- TEAEs leading to permanent discontinuation of study treatment by SOC/PT
- Fatal TEAE by SOC/PT
- AESI by AESI category ([Appendix 4](#)) and HLT/PT

The time to first AESIs (TEAE category) will be assessed by Kaplan-Meier estimates (K-M plot). In order to detect any safety signals, the hazard ratio (HR) will be provided together with the corresponding 95% confidence interval (CI) for the selected adverse events during the treatment period only. Hazard ratios will be calculated using a Cox model including treatment group and randomization strata as factors. The time is defined as the date of first specific event – the date of first dose + 1. Patients without a specific event will be censored at the end of the treatment period. Graphs of cumulative incidence rate over time may be provided by treatment group for selected TEAEs leading to permanent discontinuation of study treatment.

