**Table 1: Assignment of “as-treated” arms**

Randomized to	Treatment Received	Treatment Assignment
Dupilumab	All placebo	Placebo
Dupilumab	≥ 1 Dupilumab dose	Dupilumab
Placebo	>=1 Dupilumab dose	Dupilumab

In addition:

- Nonrandomized but treated patients will not be part of the safety population (SAF); however, their safety data will be presented separately.
- Randomized patients for whom it is unclear whether they took the study drug will be included in the safety population as randomized.

For safety summaries, three analysis periods are defined as follows:

- 16-week treatment period is defined as
  - Day 1 to the study completion date of the planned Week 16 visit (or study day 113 starting from the first dose of study drug if the date of the Week 16 treatment visit is unavailable) for those patients who completed the 16-week treatment period
  - Day 1 to the date of early termination visit, for those patients who did not complete the 16-week treatment period

- Follow-up period is defined as the date after the week 16 visit date (or study day 113 starting from the first dose of study drug if the date of Week 16 treatment visit is unavailable) to the date of the end of study visit
- Overall study Period is defined as Day 1 to the date of the end of study (EOS) visit

The SAF will be the basis for the analyses for the treatment period and overall study period; however, for the analyses for the follow-up period, only a subset of the SAF will be included, which is defined as the patients who entered the follow-up period and had at least one visit after the week 16 treatment visit (EOT).

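### Overall-study TEAE percentages pool children observed for about 16 and about 28 weeks, and the SAP neither specifies nor records dropping the protocol's optional exposure-adjusted analysis

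*SAP*

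**What the plan says.** SAP 5.7.1 has TEAE counts and proportions "summarized overall during the study, during the week 16 treatment period, and during the follow-up period separately". It adds that the "denominator for computation of percentage is the number of patients in each treatment group for the corresponding analysis period as specified in Section 3.2".

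SAP 3.2 supplies the periods and populations. "Overall study Period is defined as Day 1 to the date of the end of study (EOS) visit", and "The SAF will be the basis for the analyses for the treatment period and overall study period". Only the follow-up tables are restricted to patients who entered follow-up.

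Time under observation depends on OLE entry. SAP 2.4 states: "Patients who decline to participate in the OLE will enter a follow-up period of 12 weeks". Protocol 9.5.3.1 states: "Patients who continue into the OLE after the treatment period will not have a follow-up period".

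The same protocol section says that, "to account for potential differential exposure time, the exposure-adjusted analyses for part B may be provided", and leaves the details to the SAP. The SAP contains no patient-year rate, and its table of modifications from the protocol (1.2.3) does not mention the matter. SAP 5.5.2 derives each child's total observation time but only describes it.

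On the pandemic, SAP 5.7 says: "The summary will be performed for pre-, during, and post-COVID-19 periods for patients impacted by COVID-19, if deemed appropriate". SAP 5.3 builds those periods from each patient's own dates, with no fixed length. SAP 3.2 defines no such period.

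**The concern.** The overall-study percentage mixes two lengths of observation, about 16 and about 28 weeks. A child seen for longer has more chance of recording an event. If one arm sends fewer children into the OLE, that arm accumulates more time and shows a higher percentage with TEAEs, SAEs or AESIs at the same underlying rate.

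Unequal entry is possible because the decision follows the Week 16 outcome, on which the trial expects large differences between arms. The direction and size cannot be known from the documents, which is a reason to settle the analysis beforehand. SAP 5.7.1 lists the three periods without saying which one carries the between-arm comparison.

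**Working it through.** **Durations, checked against the plan.** Treatment is 16 weeks and follow-up 12, so 16 + 12 = 28 weeks, as in the protocol synopsis. Study days are 16 × 7 + 1 = 113 and 28 × 7 + 1 = 197, matching the schedule of events. The ratio of observation times is 28/16 = 1.75.

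**Assumptions.** The documents give neither a TEAE risk for Part B nor OLE entry by arm. I assume a constant hazard, the same in both arms, and vary the 16-week risk r16 and the entry share u. Early withdrawal is ignored.

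**Formulas.**
- h = −ln(1 − r16)/16 per week
- r28 = 1 − exp(−28h)
- Overall-study percentage = u × r16 + (1 − u) × r28

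**Worked case, r16 = 60%.** r28 = 1 − 0.4^1.75 = 79.9%.
- Entry 95% v 85%: 0.95 × 60 + 0.05 × 79.9 = 61.0%, and 0.85 × 60 + 0.15 × 79.9 = 63.0%. The gap is 2.0 points.
- Entry 90% v 60%: 0.90 × 60 + 0.10 × 79.9 = 62.0%, and 0.60 × 60 + 0.40 × 79.9 = 68.0%. The gap is 6.0 points. Mean observation is 0.9 × 16 + 0.1 × 28 = 17.2 weeks v 0.6 × 16 + 0.4 × 28 = 20.8 weeks.
- Entry 90% v 90%: 62.0% in both arms. The gap is 0.

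**Range of spurious gaps, in percentage points.**

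| 16-week risk | 28-week risk | Entry 95% v 85% | Entry 90% v 60% |
|---|---|---|---|
| 5% | 8.6% | 0.4 | 1.1 |
| 10% | 16.8% | 0.7 | 2.1 |
| 40% | 59.1% | 1.9 | 5.7 |
| 60% | 79.9% | 2.0 | 6.0 |
| 75% | 91.2% | 1.6 | 4.8 |

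With 80 children per arm, 2.0 points is 1.6 children and 0.7 points is about half a child.

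**What a patient-year rate does.** Under a constant hazard, first events divided by time to first event or end of observation equals h. At 60% risk that is 298.8 per 100 patient-years, and at 10% risk 34.4, whatever the entry share.

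**Where that rate fails.** Suppose the hazard halves after Week 16, with r16 = 10% and identical arms. In days, h = −ln(0.9)/112 = 0.000941, and the chance of a first event in the 84 follow-up days is q = 1 − exp(−0.5h × 84) = 0.0387.
- Events per child = 0.1 + (1 − u) × 0.9 × q. This gives 0.1035 at u = 90% and 0.1139 at u = 60%.
- Person-days per child = 0.1/h + (1 − u) × 0.9 × q/(0.5h). This gives 113.7 and 136.0.
- Rates are 33.2 v 30.6 per 100 patient-years, while the crude percentages are 10.4% v 11.4%. The two measures err in opposite directions.

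**COVID-19 periods.** At the 60% hazard, the expected percentage is 10.8% in a 14-day window and 55.1% in a 98-day window.

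**The case against.** A reader might infer that the SAP omitted an analysis the protocol required. It did not: the protocol wording is permissive. What stands is that the SAP neither takes up the option nor records setting it aside.

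A reader might also infer that the between-arm safety comparison is compromised. The documents do not support that. TEAEs are tabulated separately for the 16-week period, both secondary safety endpoints run through Week 16, and SAP 5.7.1 gives Kaplan-Meier estimates for first AESI and Cox hazard ratios for selected events in the treatment period only. OLE entry is summarized by arm and observation time is described, so an imbalance would be visible.

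Nor do the documents show unequal entry. Protocol 5.8 offers OLE screening to Week 16 completers in both arms, and Part B is blinded until the primary analysis. The 90% v 60% case is an illustration without documentary support.

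On COVID-19, it is tempting to say that crude percentages will be reported for windows of arbitrary length. SAP 5.7 makes those summaries conditional and names no statistic for them, and nothing presents the windows as a comparison of risk.

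Finally, a pooled rate is not free of bias. The last dose is at Week 12 and the follow-up is meant to let drug levels fall, so the hazard may change. The 33.2 v 30.6 example shows the consequence. This objection stands and limits what the rate can be used for.

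**Conclusion.** The point holds for the overall-study tables. A head-count percentage over unequal observation times depends on OLE entry as well as on risk. Under a constant hazard and equal risk in both arms, the artefact is about 2 points for common events at 95% v 85% entry and 6 points at 90% v 60%. At 5–10% risk, closer to AESIs, it is under 1 point at 95% v 85%. All of this rests on assumed entry and event rates. With equal entry the overall percentages are higher than the 16-week ones but not biased between arms.

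The 16-week safety analyses are largely unaffected, so this is an inexpensive improvement to the SAP, not a threat to its main safety conclusions.

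**What to change.** In SAP 5.7.1:
- State that the 16-week treatment period is the between-arm safety comparison.
- Label the overall-study, follow-up and any COVID-19-period TEAE tables as descriptive.
- For the overall-study summary of any TEAE, any SAE and any AESI, add patients with an event per 100 patient-years at risk beside n (%), with time running to first event or end of observation. Note that the rate assumes a roughly constant hazard, which may not hold after the last dose at Week 12.
- If COVID-19-period summaries are produced, give the person-time in each period.

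In SAP 1.2.3, record how the protocol's exposure-adjusted option has been handled.

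The cost is SAP wording, one column in the overall summary, and new derivations: SAP 5.5.2 gives only total observation time, so first-event times, and time within any COVID-19 period, must be programmed. No data collection changes.
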